10.4 Description of Statistical Methods

10.4.1

General Approach

BASICS is a phase-III Sequential, Multiple Assignment, Randomized Trial (SMART) (described fully in the Schematic of Study Design). Descriptive statistics will use percentages and counts for persons with dichotomous outcomes and means/standard deviations for continuous outcomes. For inferential tests, the p-value used for statistical significance (Type 1 error) is 0.05, and all tests are two-tailed.

10.4.2

Analysis of the Primary Efficacy Endpoint(s)

The primary efficacy endpoints include the best initial treatment for dental caries and the best treatment sequence for nonresponders. This is equivalent to the main effect of the first-stage treatment and additional clinically-relevant contrasts (see Statistical Analysis Plan for further description). Data will be analyzed according to intent to treat. The main effects will be assessed using generalized linear mixed logistic regression (for presence/absence of dental caries and presence/absence of treatment nonresponse) and negative binomial regression (for caries incidence). Predictors include semester of entry, the interaction between semester and treatment trajectory, and any relevant demographic variables. Any instance of missing data will be accounted for using time-ordered nested conditional imputation.

10.4.3

Analysis of the Secondary Endpoint(s)

Secondary endpoints in BASICS include the best dynamic treatment regime, the optimal adaptive intervention, and costs of adaptive interventions. Analysis for the best adaptive intervention will utilize weighting and replication and other methods (see Statistical Analysis Plan). Analyses for identifying the optimal adaptive intervention will use Q-Learning (see SAP).

For cost analyses, we will quantify the economic costs of dynamic treatment regimes in school-based caries prevention will using microcosting in tandem with time studies. We will take a bottom-up microcosting approach to data collection. The bottom-up approach to microcosting is characterized by quantifying resource utilization for each cost item, and then aggregating to the individual or system-level, as opposed to assessing system costs and then allocating to individual cost items (top-down approach).⁷³ This approach is more accurate for labor-intensive services than microcosting with a top-down approach.⁷⁴⁻⁷⁶ We will use the following tools to capture costs:

- 1) Standardized comprehensive templates to collect resource unit quantity and unit cost data, especially fixed costs (i.e. patient chairs, operating stools, dental lights, and other equipment), wage rates, fringe benefits, and material costs. These data templates will be filled out using retrospective administrative data (i.e. financial records, time sheets, program documents).
- 2) Time stamp data generated through the on-site clinical outcomes database, which serves to quantify the amount of time spent on clinical examinations and treatment per student. This is already built into our iPad electronic health record system.
- 3) Electronic time study logs that ask clinicians at 15-minute intervals during the workday about their current activities;⁷⁷ both clinical activities (i.e. set-up time and delivering the intervention) and research/administrative activities (i.e. staff meetings, billing/verifying insurance coverage, and downtime) can be tracked and costs captured for each type of activity.

We will take two approaches to costing-microcosting with and without the time study data. The microcosting without the time study data will combine data from the first two data collection approaches, while microcosting with the time study data will combine all three data collection approaches. Though the time stamp data captures the treatment time per child, it is unclear to what extent clinicians spend non-treatment time on activities related directly to the clinical interventions vs. research/administrative activities. Microcosting without the time study data then necessitates imposing the assumption that all the billed time by dental hygienists is related to clinical activities, making it likely that intervention costs will be overestimated across all sequential treatments. In contrast, microcosting with the time study data will allow us to precisely identify when clinicians are undertaking activities directly related to the intervention.

We will quantify intervention costs from the perspective of the agency providing dental care to schools through school-based caries prevention programs over the 2.5 years used to provide the sequential interventions. This will determine the funding needed for to set up and operate the program. We assume that the providing agency does not see students for dental care outside of the school-based caries prevention programs. We will capture the cost of dental materials and equipment, office equipment, space needs, and educational/promotional materials using internal accounting data. We will then quantify value of resources used for each patient as (resource cost*quantity used per patient). We will capture the time spent by personnel on training and delivering care through the electronic time study logs. Time costs are estimated by multiplying the time spent on activities by the U.S. Bureau of Labor Statistics for each type of personnel. The cost of healthcare resources for each treatment pathway will be estimated both at the individual patient level and by the type of sequential treatment. Because we are valuing costs over a 2.5 year timeframe, we will discount costs by 3%. We will follow validated economic evaluation checklists for quality and reproducibility.⁷⁸

We will then use multivariable regression to analyze the difference in economic costs based on responder status, providers, schools, state legislation, and observable student characteristics (i.e. race, gender). To account for missing data, which may come about if participants drop out, we will use multiple imputation to avoid eliminating cases with incomplete data. If the amount of missing or incomplete data is small (i.e. <5% of observations) and patterns of missing data are similar across intervention groups, we will additionally conduct analyses that use only complete data.

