3.2 Secondary Objectives

2. What is the most effective sequence of treatments to reduce treatment nonresponse, assessed via caries incidence?
3. What is the optimal dynamic treatment regime given patient attributes, assessed via varies incidence modified by disease severity, sociodemographics, and treatment history?
4. Given alternative strategies, what is the most cost-efficient allocation of resources that can most significantly affect population health, measured by time and cost of care?

4 Study Design and Endpoints

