4.2.2 Secondary Study Endpoints

The secondary study endpoints are costs and cost differences between sequential treatments (arithmetic means). These endpoints were selected as there is significant variation in school caries prevention program design and implementation that is unaccounted for in economic evaluations, highlighting the lack of robustness in economic studies of dental interventions.

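### The only cost model fixed in Section 10.4.3 rests on responder status and names no randomized treatment or regime, so it does not estimate the promised cost contrasts, and no stated step links cost to caries outcome

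*Protocol*

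**What the plan says.** The protocol sets the target of the cost work in several places.

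- **Section 3.2, Objective 4** asks "what is the most cost-efficient allocation of resources that can most significantly affect population health, measured by time and cost of care".
- **Section 4.2.2**: "The secondary study endpoints are costs and cost differences between sequential treatments (arithmetic means".
- **Section 10.4.3, opening**: "Secondary endpoints in BASICS include the best dynamic treatment regime, the optimal adaptive intervention, and costs of adaptive interventions". For the cost analyses it adds that "we will quantify the economic costs of dynamic treatment regimes in school-based caries prevention".
- **Section 10.4.3, on what is costed**: "The cost of healthcare resources for each treatment pathway will be estimated both at the individual patient level and by the type of sequential treatment".
- **Section 10.4.3, on the model**: "We will then use multivariable regression to analyze the difference in economic costs based on responder status, providers, schools, state legislation", and then observed child characteristics such as race and gender.

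Section 4.1 defines an adaptive intervention as a pair of pathways and says that four regimes are embedded. Section 10.4.3 names weighting and replication for finding the best adaptive intervention and refers to the SAP for that and for Q-learning. The cost text that follows is the most detailed part of the section. It names neither method and carries no such reference.

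**The concern.** The endpoint is a contrast between randomized strategies, but the one model fixed for it contains no randomized factor. Responder status is a result of first-stage treatment, recorded at Visits 2 and 3 (Section 7.3.3), and it decides who goes on to second-stage care. Its coefficient mainly says that children who are given more treatment cost more. It also averages subgroups B, C, E and F together against A and D, which blurs the very differences that Section 4.2.2 promises.

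Adding a treatment term beside responder status would not be enough. Holding response fixed removes one main route by which the first-stage choice changes cost, namely how many children need second-stage care.

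Separately, cost alone identifies the cheapest strategy. Whether a dearer strategy is worth its cost depends on the caries it prevents, and no stated step puts the two together.

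**Working it through.** **1. Promised quantity against stated model**

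| Promised | Needed in the analysis | In the stated cost regression |
|---|---|---|
| Costs of adaptive interventions (10.4.3) | Regime, each a pair of pathways (4.1) | Not listed |
| Cost differences between sequential treatments (4.2.2) | First- and second-stage assignment | Not listed |
| Most cost-efficient allocation (3.2) | Cost and caries outcome together | No step stated |

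**2. What conditioning on response removes**

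Let a responder cost 1 and a nonresponder cost *k*. With nonresponse rate *p*, the mean cost of a first-stage arm is (1 − *p*) + *pk*. For illustration, take *k* = 2 (assumed; the protocol gives no unit costs), the same in both arms, and let *p* be 0.24 in one arm and 0.36 in the other. These are the ends of the range that Section 2.1 cites from earlier school trials.

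- Arm means: 0.76 + 0.24 × 2 = 1.24 and 0.64 + 0.36 × 2 = 1.36, a difference of 0.12.
- Difference within responders: 1 − 1 = 0. Difference within nonresponders: 2 − 2 = 0.

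A model adjusted for responder status would report no arm difference here, although the arms differ by 0.12/1.24 = 9.7%. Section 10.5 assumes equal nonresponse for sample size, but the alternative hypothesis in Section 10.2 is that the arms differ.

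**3. Reproducing the planned subgroups**

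Inputs: N = 1200 (Section 5.6), 30% nonresponse (Section 10.5), equal splits at both stages (implied by the subgroup table in the Protocol Summary).

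- A and D: 1200/2 × 0.70 = 420 each. This matches.
- B, C, E and F: 1200/2 × 0.30/2 = 90 each. This matches.
- Total: 2 × (420 + 90 + 90) = 1200.

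**4. Why the combining step matters**

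Nonresponders are split between two second-stage options and responders are not, so a regime such as A+B holds only half of its arm's nonresponders.

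- Unweighted nonresponder share: 90/(420 + 90) = 17.6%.
- Weighted share (2 for responders, 4 for nonresponders, under 1:1 at both stages): 4 × 90/(2 × 420 + 4 × 90) = 360/1200 = 30%.
- A+B versus A+C, with a mean cost difference δ per nonresponder: unweighted 0.176δ, true 0.30δ, ratio 0.59. The difference would be 41% too small.
- Regime mean: unweighted (420 + 90*k*)/510, true 0.70 + 0.30*k*.

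| *k* (assumed) | Unweighted | True | Too low by |
|---|---|---|---|
| 1.5 | 1.088 | 1.150 | 5.4% |
| 2 | 1.176 | 1.300 | 9.5% |
| 3 | 1.353 | 1.600 | 15.4% |
| 4 | 1.529 | 1.900 | 19.5% |

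Two limits apply. A direct comparison of B with C (or E with F) is between re-randomized groups, needs no such weights under 1:1 allocation, and is not shrunk. And regime costs can be built correctly from the planned pathway costs, for example 0.70 × mean cost of A + 0.30 × mean cost of B under the protocol's own rate.

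**The case against.** The strongest reply is that the regression was never offered as the estimator for Objective 4. The text first costs the pathways and only then runs the regression. Its covariates (providers, schools, legislation, child characteristics) read like a study of what drives cost. That reading is fair, but it leaves the promised contrast with no stated model, and the text does not call the regression descriptive.

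Two stronger readings are tempting, and the documents support neither.

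- A reader might infer that the plan compares raw, unweighted means and so yields biased regime costs. The endpoint says only that means are arithmetic, the usual summary for cost. Nothing says they are unweighted or that A and B will be pooled.
- A reader might infer that the adaptive interventions are not costed at all. Section 10.4.3 states that aim twice and collects cost by patient and by pathway.

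It can also be said that weighting for cost is SAP material. That stands: its absence from the protocol alone is no finding. What the protocol does fix is a covariate list without the randomized factors.

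Finally, Objective 4 says it is measured by time and cost of care, effectiveness falls under the other objectives, and Section 10.4.3 commits to economic evaluation checklists. This partly stands. The mismatch lies partly in the objective's wording, and narrowing that wording is a legitimate remedy.

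**Conclusion.** The point holds in a limited form. The one cost model that the protocol specifies is built on a post-randomization variable and omits both randomized treatments and the regime. It therefore does not estimate the costs of the adaptive interventions or the cost differences between sequential treatments. No stated step connects cost to caries outcome, so the cost-efficiency question in Objective 4 is not answered as worded.

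No bias has been shown. The 17.6% against 30% and the factor of 0.59 follow from the protocol's planned cells, and only if pathways are pooled without weights. The 5% to 20% shortfall in a regime mean needs, in addition, assumed cost ratios of 1.5 to 4. These figures show why the weighting step deserves a sentence. They do not describe what the plan says it will do. For a secondary endpoint, this should be corrected before cost data are analysed.

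**What to change.** In Section 10.4.3 and the SAP:

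1. Make the main cost analysis a comparison by assigned first-stage treatment and by embedded regime, without conditioning on responder status.
2. Use the same weighting and replication as the regime outcome analysis. Each responder is consistent with two regimes and must be replicated across both. Take the weights from the actual assignment probabilities, because Section 10.6.1 specifies adaptive randomization. Weights of 2 and 4 are right only if allocation is 1:1 at both stages.
3. Keep the responder-status regression and label it descriptive.
4. Report cost and nonresponse at the outcome visits together for each regime, for example incremental cost per nonresponse averted with a bootstrap interval that resamples children so that cost and outcome stay paired. Otherwise, narrow Objective 4 to cost alone.

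This costs a few lines of text. The patient-level costs, assignments and outcomes are already to be collected, so no new data are needed.

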10.4.4 Safety Analyses

Adverse events will be summarized using descriptive statistics during treatment. No other safety endpoints are included. AEs will be coded following the Medical Dictionary for Regulatory Activities and counted only once for a given participant. Frequencies and severities will be presented, including when the AE was documented. AEs will be ascertained by the study clinician and reported by the PI to the IRB.

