8.1.1 Definition of Adverse Events (AE)

An **adverse event** (AE) is any symptom, sign, illness or experience that develops or worsens in severity during the course of the study. Intercurrent illnesses or injuries should be regarded as adverse events. Abnormal results of diagnostic procedures are considered to be adverse events if the abnormality:

- results in study withdrawal
- is associated with a serious adverse event
- is associated with clinical signs or symptoms
- leads to additional treatment or to further diagnostic tests
- is considered by the investigator to be of clinical significance

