8.3 Time Period and Frequency for Event Assessment and Follow-Up

The occurrence of an AE or SAE may come to the attention of study personnel during study visits and interviews of a study participant presenting for medical care, or upon review by a study monitor. All AEs including local and systemic reactions not meeting the criteria for SAEs will be captured on the appropriate RF. Information to be collected includes event description, time of onset, clinician's assessment of severity, relationship to study product (assessed only by those with the training and authority to make a diagnosis), and time of resolution/stabilization of the event. All AEs occurring while on study must be documented appropriately regardless of relationship. All AEs will be followed to adequate resolution.

Any medical condition that is present at the time that the participant is screened will be considered as baseline and not reported as an AE. However, if the study participant's condition deteriorates at any time during the study, it will be recorded as an AE. UPs will be recorded in the data collection system throughout the study.

Changes in the severity of an AE will be documented to allow an assessment of the duration of the event at each level of severity to be performed. AEs characterized as intermittent require documentation of onset and duration of each episode.

The PI will record all reportable events with start dates occurring any time after informed consent is obtained until 7 (for non-serious AEs) or 30 days (for SAEs) after the last day of study participation. At each study visit, the investigator will inquire about the occurrence of AE/SAEs since the last visit. Events will be followed for outcome information until resolution or stabilization.

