8.4.2 Serious Adverse Event Reporting

SAEs that are unanticipated, serious, and possibly related to the study intervention will be reported to the IRB and PCORI in accordance with requirements:

- Unexpected fatal or life-threatening AEs related to the intervention will be reported to the Medical Monitor within 3 days of the investigator becoming aware of the event. Other serious and unexpected AEs related to the intervention will be reported within 7 days.
- Anticipated or unrelated SAEs will be handled in a less urgent manner but will be reported to the IRB in accordance with their requirements and will be reported to NIH on an annual basis.
- All other AEs documented during the course of the trial will be reported to NIH on an annual basis by way of inclusion in the annual report and in the annual AE/DSMP summary which will be provided to NIH.

We note that no clinical adverse events are expected.

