10.5 Sample Size

Sample size calculations for Objective 1 are computed for the main effects of the specified experimental design, including the main effects for first-stage treatment (A+B+C vs D+E+F) and the main effects for second-stage treatment in nonresponders (B+E vs C+F). These main effects are equivalent to a longitudinal comparison of two parallel groups in a randomized trial [45]. We assume a within-person correlation of 0.5, a study drop-out rate of 10% (with the difference offset by newly enrolled children each year), a desired power of 0.85, and an alpha of 0.05. This yields a total sample size of 122 for a medium effect size (Cohen's $d=0.5$). As a result, our anticipated

sample size is sufficient for even small to medium effects at acceptable power levels. We subsequently propose sampling more subjects to support investigation of effect modifiers or subgroup comparisons (e.g., A+B, A+C, D+E). For second-stage treatment main effects, additional considerations are needed for the rate of nonresponse [45]. We assume nonresponse rates are equal across first-stage treatment assignments, and further assume an average nonresponse rate of 30% (as informed by prior studies). This yields a total N of $122/0.3 = 406$, or N=203 for first-stage treatment groups and 101 in each nonresponse group (B+E and C+F).

For Objective 2, we estimate power based on the Multiple Comparisons with the Best (MCB) methodology for comparing our embedded DTRs while accounting for multiple comparisons, thereby increasing power [46]. We assume a type 1 error rate, now viewed as the probability of excluding the best DTR from the set of all DTRs, of 5%. We estimate the expected power given our anticipated final sample size assuming the same 10% yearly dropout rate (N=840) for four DTRs, with a minimum effect size of 0.1: $Power_{\alpha,n}(\Sigma, \Delta, \Delta_{min}) \geq 1 - \beta$. We assume the most conservative case as possible by setting all other DTRs to be the minimum detectable effect size away, compared to DTR(1) ($\Delta_i = \Delta_{min}$). We also assume that correlations between DTRs are equal, in keeping with recommendations. This yields a power of >99%, and the study is well powered even for exceedingly small effect size differences. Finally, as optimization using Q-learning is considered hypothesis generating in the SMART framework, we do not estimate power for this analysis.

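### The adverse event rules do not exempt the caries endpoint, and the once-per-participant count in 10.4.4 has no stated unit and drops same-term repeats across treatment stages

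*Protocol*

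**What the plan says.** **What is an AE.** Protocol 8.1.1 says an AE "is any symptom, sign, illness or experience that develops or worsens in severity during the course of the study". An abnormal diagnostic result also qualifies if, among other triggers, it "leads to additional treatment or to further diagnostic tests".

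**What is recorded.** Protocol 8.3 says: "All AEs occurring while on study must be documented appropriately regardless of relationship". A condition already present at screening "will be considered as baseline and not reported as an AE", but "if the study participant's condition deteriorates at any time during the study, it will be recorded as an AE". Section 8.4.1 sends AEs to the IRB irrespective of relationship. Section 7.3.3 has AEs seen by the investigator recorded at the same visits as the oral examination.

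**What is expected.** Protocol 8.4.2: "We note that no clinical adverse events are expected".

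**What is summarized.** Protocol 10.4.4 codes AEs in MedDRA, has them "counted only once for a given participant", and presents frequencies, severities and time of documentation. It adds no other safety endpoint.

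**What the endpoint is.** Under 7.1.1, nonresponse means new caries on sound posterior teeth, baseline caries that did not arrest, or an atraumatic restoration that was not retained. Nonresponse at Visit 2 or 3 leads to second-stage randomization and treatment (7.3.3).

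**The concern.** The trial's main efficacy failure, a new cavity, fits its own AE definition, and no sentence separates the two. Clinicians must either file cavities as AEs, with follow-up and IRB reporting, or decide individually not to. They are unblinded (10.6.1), so that choice could differ by arm. If cavities are filed, a summary of participants with at least one AE would mostly restate the efficacy result.

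The counting rule adds a second problem. Children who are re-randomized receive a first-stage and then a second-stage treatment, and the protocol reuses agents across the stages. A once-per-participant count with no stage in it cannot show a reaction that recurs after the second-stage treatment. The AE summary is the only safety analysis described in section 10.

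**Working it through.** **Step 1: reproduce the planned numbers.** Inputs: 1200 children (Protocol Summary), and section 10.5, which says the planners "further assume an average nonresponse rate of 30" per cent.

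- Nonresponders: 1200 × 0.30 = 360.
- Per second-stage subgroup (B, C, E, F): 360 / 4 = 90, as in the subgroup table.
- Responders per first-stage arm: 600 × 0.70 = 420, as in the table for A and D.

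**Step 2: set each route to nonresponse against the AE rules.**

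| Route to nonresponse (7.1.1) | AE under 8.1.1 and 8.3? |
|---|---|
| New caries on a sound tooth | Yes. It developed on study, and at Visits 2 and 3 it leads to added treatment. The baseline exemption does not apply. |
| Baseline lesion not arrested | Not necessarily. It was present at screening, and failure to arrest need not mean deterioration. |
| Atraumatic restoration not retained | Not necessarily. 7.1.1 counts it as nonresponse because new decay cannot be ruled out. |

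Only the first route is clearly an AE, so 360 is an upper bound for children with a caries AE by Visit 3. The documents do not split nonresponse by route. For scale, the 24% to 36% of children with new caries in earlier school trials (2.1) would give 1200 × 0.24 = 288 to 1200 × 0.36 = 432 children. Either way this conflicts with 8.4.2.

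**Step 3: the two readings of the counting rule.**

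- *Once per coded term.* A cavity at Visit 2 and irritation at Visit 3 are different terms, and both count. Irritation after first-stage silver diamine fluoride (SDF) and again after its reapplication is one count, which stays with the first stage.
- *Once per child.* Any reaction after a recorded caries AE is lost.

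Repeats of a term are foreseeable. In 7.1.1 both second-stage options after SDF include SDF reapplication, one option after sealants is sealant reapplication, and continued nonresponse leads to the second-stage treatment being repeated.

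**Step 4: illustration of second-stage reactions lost among 360 children.** Let *p* be the reaction risk per stage (assumed, same term, independent between stages). Let *f* be the share of nonresponders with a prior caries AE (assumed).

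- Per child: 360 × *p* × [*f* + (1 − *f*) × *p*]
- Per term: 360 × *p*²

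| *p* | Second-stage reactions | Lost per child, *f* = 1 | Lost per child, *f* = 0.5 | Lost per term |
|---|---|---|---|---|
| 1% | 3.6 | 3.6 | 1.8 | 0.04 |
| 5% | 18 | 18 | 9.5 | 0.9 |
| 10% | 36 | 36 | 19.8 | 3.6 |

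**Step 5: illustration over all visits.** With per-visit risk *p* and six treatment visits, the share of same-term events lost is 1 − [1 − (1 − *p*)⁶] / (6*p*).

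- *p* = 2%: 1 − 0.1142/0.12 = 5%
- *p* = 5%: 1 − 0.2649/0.30 = 12%
- *p* = 10%: 1 − 0.4686/0.60 = 22%

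These rates are assumed, and six visits is the maximum: the subgroup table lists A and D (840 children) as single application, although 6.1.9 and 6.3.1 allow repeats.

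**The case against.** The strongest reply is that 10.4.4 speaks of coded AEs, so the ordinary reading is each term once per participant. A one-AE-per-child rule would leave MedDRA coding and frequencies with little purpose. This stands. A reader might infer that every later reaction in re-randomized children goes uncounted. The wording permits that but does not say it, and on the ordinary reading only repeats of the same term are lost.

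A reader might also infer that a between-arm comparison of reactions loses power because cavities dilute it. The protocol plans descriptive AE summaries and no such test, and in a coded table a local reaction keeps its own row. Nor does every nonresponder have an AE by definition, as Step 2 shows.

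It is also fair that the rule limits only the summary. Onset, severity and relationship are recorded (8.2.2, 8.3), the time of documentation is presented (10.4.4), individual reporting continues (8.4), and SDF staining and varnish allergy are reviewed quarterly (8.8). Stage could be reconstructed from these data, but none of these provisions calls for a count by stage.

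Finally, table layout normally belongs to the SAP, and its absence from the protocol is no fault. But 10.4.4 does not defer to the SAP, unlike 10.4.6 to 10.4.9; it fixes a counting rule. The AE definition also governs recording from consent onward, so a SAP finished before database lock (10.1) comes too late to correct what was captured.

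**Conclusion.** The point holds in two limited parts.

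1. Sections 8.1.1 and 8.3 do not exempt the efficacy endpoint and conflict with 8.4.2. At 30% nonresponse, at most about 360 of 1200 children would carry a caries AE by Visit 3. The true figure depends on how much nonresponse is new caries. If these are recorded, efficacy failures would probably dominate any count of participants with an AE.

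2. The once-per-participant rule in 10.4.4 has no stated unit. On the usual per-term reading the loss is confined to same-term repeats and is small at low reaction risks: about 1 of 18 second-stage reactions at an assumed 5%. What is lost is the recurrence after second-stage treatment, which a by-stage summary needs. On the per-child reading, any reaction after a recorded AE disappears.

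All reaction rates used here are assumptions; the protocol gives none. The finding concerns recording and summary, and does not show that individual safety events would go unreported.

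**What to change.** - Reconcile 8.1.1 and 8.3 with 8.4.2. State that caries captured as the efficacy endpoint is not recorded as an AE unless accompanied by a complication such as pain, abscess or infection.
- In 10.4.4, count each MedDRA preferred term once per participant per treatment stage, at maximum severity. Use as denominator the children treated in that stage, tabulated by treatment received.
- Also give the total number of events, so that repeats within a stage remain visible.

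This costs a few sentences in the protocol and a slightly longer AE table. Onset, severity and visit are already collected, so no new data are needed. The AE definition should be settled before the first treatment visit, because it determines what is recorded.
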